## **6.0 REGISTRATION PROCEDURES**

### **6.1 GENERAL GUIDELINES FOR DF/HCC INSTITUTIONS**

Institutions will register eligible participants in the Clinical Trials Management System (CTMS) OnCore. Registrations must occur prior to the initiation of protocol therapy. Any participant not registered to the protocol before protocol therapy begins will be considered ineligible and registration will be denied.

An investigator will confirm eligibility criteria and a member of the study team will complete the protocol-specific eligibility checklist.

Following registration, participants may begin protocol therapy. Issues that would cause treatment delays should be discussed with the Overall Principal Investigator (PI). If a participant does not receive protocol therapy following registration, the participant's registration on the study must be canceled. Registration cancellations must be made in OnCore as soon as possible.

#### **Registration Process for DF/HCC Institutions**

DF/HCC Standard Operating Procedure for Human Subject Research Titled *Subject Protocol Registration* (SOP #: REGIST-101) must be followed.

#### **General Guidelines for Other Investigative Sites**

Eligible participants will be entered on study centrally by the Coordinating Center. All sites should call the Coordinating Center to verify slot availabilities.

Following registration, participants should begin protocol treatment within 14 days of registration. Issues that would cause treatment delays should be discussed with the Principal Investigator/Sponsor. If a participant does not receive protocol therapy following registration, the participant's registration on the study must be canceled. The Coordinating Center should be notified of cancellations as soon as possible.

---

## Registration Process for Other Investigative Sites

To register a subject, the following documents should be completed by the participating institution and forwarded to the Coordinating Center:

- Copy of source documentation for inclusion/exclusion criteria and screening procedures, including but not limited to
  - Pathology report
  - Medical history and physical exam
  - Laboratory reports
  - Concomitant medication list
- Demographics information.
- Signed study consent form.
- Study Entry Note
- HIPAA authorization form, if applicable
- Eligibility checklist

The Coordinating Center will review the above documentation to confirm eligibility and consent. To complete the registration process, the Coordinating Center will follow DF/HCC Standard Operating Procedure for Human Subject Research Titled *Subject Protocol Registration* (SOP #: REGIST-101) and register the participant on the protocol. Once registered a confirmation email with the participant study number, and if applicable the dose treatment level, will be sent to the participating site.

NOTE: Registrations can only be conducted by the Coordinating Center during the business hours of 8:30 AM and 5:00 PM Eastern Standard Time (or Eastern Daylight Time when applicable), Monday through Friday. A complete registration packet, including all documents listed above, must be received at least 1 business day *prior to* the anticipated registration to ensure adequate review. Same day treatment registrations will only be accepted with prior notice and discussion with the DF/HCC Lead Institution.

**Treatment may not begin without confirmation from the Coordinating Center that the participant has been registered.**

## 7.0 TREATMENT PLAN

### 7.1 Treatment Regimen

The treatment to be used in this trial is outlined below in Table 2.

---

CONFIDENTIAL

*This document is confidential. Do not disclose or use unless authorized.*

*Table 2: Trial Treatment*

Drug	Dose/ Potency	Dose Frequency	Route of Administration	Regimen/Treatment Period	Use
Pembrolizumab	200mg*	Q3W	IV infusion	Day 1 of each 3 week cycle	Experimental

\* For the pediatric population, the dose is 2 mg/kg up to a maximum of 200 mg

## 7.1.1 Dose Selection/Modification

### 7.1.1.1 Dose Selection

The rationale for selection of doses to be used in this trial is provided in Section 4.0 – Background and Rationale.

Details on preparation and administration of pembrolizumab are provided in the Pharmacy Manual.

### 7.1.1.2 Dose Modification

Adverse events (both non-serious and serious) associated with pembrolizumab exposure may represent an immunologic etiology. These adverse events may occur shortly after the first dose or several months after the last dose of treatment. Pembrolizumab must be withheld for drug-related toxicities and severe or life-threatening AEs as per Table 3 below. See Section 7.5.1 and Events of Clinical Interest (ECI) Guidance Document (Appendix E) for supportive care guidelines, including use of corticosteroids.

*Table 3: Dose Modification Guidelines for Drug-Related Adverse Events*

Toxicity	Hold Treatment For Grade	Timing for Restarting Treatment	Discontinue Subject
Diarrhea/Colitis	2-3	Toxicity resolves to Grade 0-1.	Toxicity does not resolve within 12 weeks of last dose or inability to reduce corticosteroid to 10 mg or less of prednisone or equivalent per day within 12 weeks.
	4	Permanently discontinue	Permanently discontinue
AST, ALT, or Increased Bilirubin	2	Toxicity resolves to Grade 0-1	Toxicity does not resolve within 12 weeks of last dose.
	3-4	Permanently discontinue (see exception below) 	Permanently discontinue
Type 1 diabetes mellitus (if new onset) or Hyperglycemia	T1DM or 3-4	Hold pembrolizumab for new onset Type 1 diabetes mellitus or Grade 3-4 hyperglycemia associated with evidence of beta cell failure.	Resume pembrolizumab when patients are clinically and metabolically stable.
Hypophysitis	2-3	Toxicity resolves to Grade 0-1	Toxicity does not resolve within 12 weeks of last dose or inability to reduce corticosteroid to 10 mg or less of prednisone or equivalent per day within 12 weeks.
	4	Permanently discontinue	Permanently discontinue

*CONFIDENTIAL*

*This document is confidential. Do not disclose or use unless authorized.*

Toxicity	Hold Treatment For Grade	Timing for Restarting Treatment	Discontinue Subject
Hyperthyroidism	3	Toxicity resolves to Grade 0-1	Toxicity does not resolve within 12 weeks of last dose or inability to reduce corticosteroid to 10 mg or less of prednisone or equivalent per day within 12 weeks.
	4	Permanently discontinue	Permanently discontinue
Hypothyroidism	2-4	Therapy with pembrolizumab can be continued while treatment for the thyroid disorder is instituted	Therapy with pembrolizumab can be continued while treatment for the thyroid disorder is instituted.
Infusion Reaction	3-4	Permanently discontinue	Permanently discontinue
Pneumonitis	2	Toxicity resolves to Grade 0-1	Toxicity does not resolve within 12 weeks of last dose or inability to reduce corticosteroid to 10 mg or less of prednisone or equivalent per day within 12 weeks.
	3-4	Permanently discontinue	Permanently discontinue
Renal Failure or Nephritis	2	Toxicity resolves to Grade 0-1	Toxicity does not resolve within 12 weeks of last dose or inability to reduce corticosteroid to 10 mg or less of prednisone or equivalent per day within 12 weeks.
	3-4	Permanently discontinue	Permanently discontinue
All Other Drug-Related Toxicity 	3 or Severe	Toxicity resolves to Grade 0-1	Toxicity does not resolve within 12 weeks of last dose or inability to reduce corticosteroid to 10 mg or less of prednisone or equivalent per day within 12 weeks.
	4	Permanently discontinue	Permanently discontinue

**Note: Permanently discontinue for any severe or Grade 3 drug-related AE that recurs or any life-threatening event.**

 For patients with liver metastasis who begin treatment with Grade 2 AST or ALT, if AST or ALT increases by greater than or equal to 50% relative to baseline and lasts for at least 1 week then patients should be discontinued.

 Patients with intolerable or persistent Grade 2 drug-related AE may hold study medication at physician discretion. Permanently discontinue study drug for persistent Grade 2 adverse reactions for which treatment with study drug has been held, that do not recover to Grade 0-1 within 12 weeks of the last dose.

Dosing interruptions are permitted in the case of medical / surgical events or logistical reasons not related to study therapy (e.g., elective surgery, unrelated medical events, patient vacation, and/or holidays). Subjects should be placed back on study therapy within 3 weeks of the scheduled interruption, unless otherwise discussed with the Sponsor. The reason for interruption should be documented in the patient's study record.

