#### **7.5 Rescue Medications & Supportive Care**

##### **7.5.1 Supportive Care Guidelines**

Subjects should receive appropriate supportive care measures as deemed necessary by the treating investigator. Suggested supportive care measures for the management of adverse events with potential immunologic etiology are outlined below and in greater detail in the ECI guidance document. Where appropriate, these guidelines include the use of oral or intravenous treatment with corticosteroids as well as additional anti-inflammatory agents if symptoms do not improve with administration of corticosteroids. Note that several courses of steroid tapering may be necessary as symptoms may worsen when the steroid dose is decreased. For each disorder, attempts should be made to rule out other causes such as metastatic disease or bacterial or viral

---

*CONFIDENTIAL*

*This document is confidential. Do not disclose or use unless authorized.*

infection, which might require additional supportive care. The treatment guidelines are intended to be applied when the investigator determines the events to be related to pembrolizumab.

Note: if after the evaluation the event is determined not to be related, the investigator is instructed to follow the ECI reporting guidance but does not need to follow the treatment guidance (as outlined in the ECI guidance document). Refer to Section 7.1.1 for dose modification.

It may be necessary to perform conditional procedures such as bronchoscopy, endoscopy, or skin photography as part of evaluation of the event. Suggested conditional procedures, as appropriate, can be found in the ECI guidance document.

- **Pneumonitis:**

- For **Grade 2 events**, treat with systemic corticosteroids. When symptoms improve to Grade 1 or less, steroid taper should be started and continued over no less than 4 weeks.
- For **Grade 3-4 events**, immediately treat with intravenous steroids. Administer additional anti-inflammatory measures, as needed.
- Add prophylactic antibiotics for opportunistic infections in the case of prolonged steroid administration.

- **Diarrhea/Colitis:**

Subjects should be carefully monitored for signs and symptoms of enterocolitis (such as diarrhea, abdominal pain, blood or mucus in stool, with or without fever) and of bowel perforation (such as peritoneal signs and ileus).

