### 7.7 Criteria for Removal from Protocol Treatment

Subjects may withdraw consent for protocol treatment and/or study itself at any time for any reason or be removed from the protocol treatment and/or study itself at the discretion of the investigator should any untoward effect occur. In addition, a subject may be withdrawn by the treating investigator or the Sponsor if enrollment into the trial is inappropriate, the trial plan is violated, or for administrative and/or other safety reasons. Specific details regarding discontinuation or withdrawal are provided in Section 10.1.4: Other Procedures.

Treatment may continue until one of the following criteria applies:

- The subject withdraws consent to treatment.
- Confirmed radiographic disease progression

*NOTE: A subject may be granted an exception to continue on treatment with confirmed radiographic progression if clinically stable or clinically improved*

- Unacceptable adverse experiences as described in Section 7.1.1
- Intercurrent illness that prevents further administration of treatment
- Investigator's decision to withdraw the subject
- The subject has a confirmed positive serum pregnancy test
- Noncompliance with trial treatment or procedure requirements
- The subject is lost to follow-up
- Completed 24 months of uninterrupted treatment with pembrolizumab or 35 administrations of study medication, whichever is later.

*NOTE: 24 months of study medication is calculated from the date of first dose. Subjects who stop pembrolizumab after 24 months may be eligible for up to one year of additional study treatment if they progress after stopping study treatment provided they meet the requirements detailed in Section 10.1.5.5*

- Treatment was held for 9 weeks for reasons other than complete response
- Administrative reasons

---

CONFIDENTIAL

*This document is confidential. Do not disclose or use unless authorized.*

Participants will be removed from the protocol therapy when any of these criteria apply. Participants removed from protocol therapy for unacceptable adverse event(s) will be followed until resolution or stabilization of the adverse event. Alternative care options will be discussed with the participant.

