Exposure	Is there evidence that the subject was actually exposed to the Merck product such as: reliable history, acceptable compliance assessment (pill count, diary, etc.), expected pharmacologic effect, or measurement of drug/metabolite in bodily specimen?							
Time Course	Did the AE follow in a reasonable temporal sequence from administration of the Merck product? Is the time of onset of the AE compatible with a drug-induced effect (applies to trials with investigational medicinal product)?							
Likely Cause	Is the AE not reasonably explained by another etiology such as underlying disease, other drug(s)/vaccine(s), or other host or environmental factors							

CONFIDENTIAL

*This document is confidential. Do not disclose or use unless authorized.*

Relationship to Merck product (continued)	The following components are to be used to assess the relationship between the test drug and the AE: (continued)	
	Dechallenge	Was the Merck product discontinued or dose/exposure/frequency reduced? If yes, did the AE resolve or improve? If yes, this is a positive dechallenge. If no, this is a negative dechallenge. (Note: This criterion is not applicable if: (1) the AE resulted in death or permanent disability; (2) the AE resolved/improved despite continuation of the Merck product; or (3) the trial is a single-dose drug trial); or (4) Merck product(s) is/are only used one time.)
Rechallenge	Was the subject re-exposed to the Merck product in this study? If yes, did the AE recur or worsen? If yes, this is a positive rechallenge. If no, this is a negative rechallenge. (Note: This criterion is not applicable if: (1) the initial AE resulted in death or permanent disability, or (2) the trial is a single-dose drug trial); or (3) Merck product(s) is/are used only one time). NOTE: IF A RECHALLENGE IS PLANNED FOR AN ADVERSE EVENT WHICH WAS SERIOUS AND WHICH MAY HAVE BEEN CAUSED BY THE MERCK PRODUCT, OR IF REEXPOSURE TO THE MERCK PRODUCT POSES ADDITIONAL POTENTIAL SIGNIFICANT RISK TO THE SUBJECT, THEN THE RECHALLENGE MUST BE APPROVED IN ADVANCE BY THE U.S. CLINICAL MONITOR AS PER DOSE MODIFICATION GUIDELINES IN THE PROTOCOL.	
	Consistency with Trial Treatment Profile	Is the clinical/pathological presentation of the AE consistent with previous knowledge regarding the Merck product or drug class pharmacology or toxicology?

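### Section 10.1.1.11 takes a patient off treatment for any toxicity interruption, contradicting the 8 of 10 Table 3 rows that hold and restart; the diabetes row also lacks a carve-out for life-threatening episodes

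*Combined protocol and SAP*

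**What the plan says.** **Toxicity interruptions.** Section 7.1.1.2 opens with "Pembrolizumab must be withheld for drug-related toxicities and severe or life-threatening AEs as per Table 3 below". Table 3 then gives, for each toxicity, the grades at which to hold, the condition for restarting, and when to stop for good. Footnote 2 lets the physician hold for intolerable or persistent Grade 2 drug-related events, and requires permanent discontinuation only if the event has not recovered within 12 weeks of the last dose. Section 7.7 lists the criteria that end treatment. Among them are "Unacceptable adverse experiences as described in Section 7.1.1" and a hold of 9 weeks for reasons other than complete response.

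Section 10.1.1.11 (Trial Compliance) states a different rule: an interruption of the treatment plan for toxicity means that the patient comes off treatment. It has no grade limit, no time limit and no reference to Table 3.

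**Diabetes.** The Table 3 row says "Hold pembrolizumab for new onset Type 1 diabetes mellitus or Grade 3-4 hyperglycemia associated with evidence of beta cell failure" and then "Resume pembrolizumab when patients are clinically and metabolically stable". The Note beneath the table says "Permanently discontinue for any severe or Grade 3 drug-related AE that recurs or any life-threatening event". Section 7.5.1 counts diabetic ketoacidosis within this event, and Table 6 describes Grade 4 as having life-threatening consequences.

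**Stopping rule.** Under Section 7.1.4 the study stops if more than 30% of patients discontinue pembrolizumab because of an adverse event, or on any toxicity-related death.

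**The concern.** A site that applies 10.1.1.11 as written would permanently withdraw a patient with, for example, Grade 2 pneumonitis or a Grade 2 transaminase rise, although Table 3 says to restart on recovery to Grade 0-1. A site that applies Table 3 breaches 10.1.1.11. Two sites could treat the same event in opposite ways, each with a section of the protocol to cite.

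The patient who is withdrawn loses further treatment. The trial may record a discontinuation due to an adverse event that Table 3 would have recorded as a temporary hold, and such discontinuations are what the 30% rule counts.

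The diabetes question is narrower but concerns re-dosing after a life-threatening event. A patient whose life-threatening ketoacidosis is later controlled on insulin meets the row's condition for resuming and also falls under the Note's instruction to stop.

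**Working it through.** No power or error-rate calculation applies. The check is a row count, a time comparison, the stopping-rule threshold, and a reading of the diabetes row against the Note.

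**1. Table 3, row by row**

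| Row | Hold and restart | Permanent stop by grade | Contradicted by 10.1.1.11 |
|---|---|---|---|
| Diarrhea/colitis | Grade 2-3 | Grade 4 | yes |
| AST, ALT or bilirubin | Grade 2 | Grade 3-4 | yes |
| T1DM/hyperglycemia | T1DM or Grade 3-4 | none | yes |
| Hypophysitis | Grade 2-3 | Grade 4 | yes |
| Hyperthyroidism | Grade 3 | Grade 4 | yes |
| Hypothyroidism | none (may continue, Grade 2-4) | none | no |
| Infusion reaction | none | Grade 3-4 | no |
| Pneumonitis | Grade 2 | Grade 3-4 | yes |
| Renal failure/nephritis | Grade 2 | Grade 3-4 | yes |
| All other | Grade 3 or severe | Grade 4 | yes |

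Rows with a hold-and-restart step: 10 − 2 = 8. Rows that stop permanently at Grade 4: also 8, but a different set (all except T1DM/hyperglycemia and hypothyroidism).

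**2. Do Section 7.7 and Table 3 agree with each other?** Most hold rows allow 12 weeks from the last dose for recovery; Section 7.7 ends treatment after a 9-week hold. On the 3-week schedule, a hold begins when the next dose falls due, 3 weeks after the last one. Then 3 + 9 = 12 weeks from the last dose. The two limits match, provided the hold is counted from the missed dose. Both allow holding, so 10.1.1.11 is the outlier.

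**3. The 30% rule.** Section 7.1.4 does not state its denominator. With the 22 planned adults, 0.30 × 22 = 6.6, so the seventh discontinuation crosses the limit. With the 11 first-stage patients, 0.30 × 11 = 3.3, so the fourth does. With counts this small, a few holds turned into withdrawals could matter. The documents give no rate from which to say how many there would be.

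**4. The diabetes row against the Note**

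- The row covers new-onset T1DM without a grade limit and hyperglycemia at Grade 3-4. It has no branch for life-threatening episodes.
- The Note's first limb (a Grade 3 event that recurs) has work to do only if it overrides rows that allow restart after Grade 3: diarrhea/colitis, hypophysitis, hyperthyroidism and all other. That suggests the Note overlays the rows.
- The second limb covers any life-threatening event. Since 8 of 10 rows already stop at Grade 4, it adds something mainly for diabetes and hypothyroidism.
- Section 7.7 makes removal mandatory when one of its criteria applies, including the one that refers to 7.1.1, and always permits the investigator to withdraw a patient.
- Section 7.5.1 does not rank row against Note. It says "Refer to Section 7.1.1 for dose modification", and its diabetes text covers insulin and work-up only.
- Table 6 adds a safeguard for a planned rechallenge after a serious event that the drug may have caused: "THEN THE RECHALLENGE MUST BE APPROVED IN ADVANCE BY THE U.S. CLINICAL MONITOR AS PER DOSE MODIFICATION GUIDELINES IN THE PROTOCOL". It does not say which dose-modification text the approver should apply.

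**The case against.** **On 10.1.1.11.** The sentence sits under a compliance heading, and an experienced site would follow Table 3 and Section 7.7. That is likely, but nothing gives those sections priority, and either course breaches a stated rule. One could also read the sentence as a deliberate counterpart to Section 7.1.1.2, which permits short interruptions for reasons unrelated to study therapy. That reading fails: Table 3 has a column for restarting after toxicity, and footnote 2 and Section 7.7 set time limits on holds.

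**On diabetes.** A reader might infer that no dosing decision can satisfy both the row and the Note. The documents do not support that. Stopping is always allowed under Section 7.7 and is mandatory if the Note applies. The instruction to resume can be read as a condition for restarting, not a duty to re-dose. Nor can a site re-dose on its own reading, because Table 6 requires prior approval. What stands is that the row has no exception and the reader must infer the ranking. The hepatic row, by contrast, marks its exception expressly.

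**On the unseen guidance.** Section 7.5.1 describes its measures as "outlined below and in greater detail in the ECI guidance document". That document (Appendix E) is not among the supplied text and could settle the diabetes question. The point is therefore limited to the supplied text.

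**Conclusion.** The wording of 10.1.1.11 is wrong as it stands. It contradicts 8 of 10 Table 3 rows, footnote 2 and the 9-week limit in Section 7.7, and followed literally it ends treatment where the dose-modification table restarts it. It should be corrected. The possible effect on the 30% rule assumes that such withdrawals would be recorded as adverse-event discontinuations. No frequency is available, so it cannot be said that the rule would be triggered.

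The diabetes point is secondary: 1 of 10 rows, life-threatening episodes only. The better reading favours stopping, but it is not written down. The hypothyroidism row has a milder version at Grade 4, where continuing is permitted but not directed, so stopping satisfies both texts.

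A reader might also infer that the response-rate test is compromised. The documents do not support that. The two-stage boundaries do not depend on these texts, the efficacy population is all eligible adults who begin treatment, and Section 7.9 keeps patients who stop for a drug-related event in the evaluable count. The column in which the diabetes row's resume instruction appears may be an artefact of text extraction, and nothing here rests on it.

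**What to change.** **Section 10.1.1.11.** Replace the sentence with: *Interruptions due to toxicity are managed per Table 3; subjects are withdrawn only when Table 3 or Section 7.7 requires it (held 9 weeks, i.e. 12 weeks from last dose on the 3-week schedule).* Add a reference to Table 4, which has its own stopping rule for infusion reactions.

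**Table 3, default.** Add to the diabetes row: *life-threatening events: permanently discontinue (see Note)*. Limit the hypothyroidism row to events that are not life-threatening.

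**Table 3, alternative.** If the sponsor intends resumption after control on insulin or hormone replacement, write that as an express exception in the Note, subject to the Table 6 approval. This should not be the default, because it loosens a safety rule and the documents offer no support for doing so.

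In either case, check that Appendix E agrees with the chosen wording. The cost is one sentence and two short row edits (or one clause in the Note), with no added procedures or patients.
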